4.4 Efficacy and Safety Variables

4.4.1 Efficacy Variables

The efficacy variables in this study include EZ area (i.e., area of IS/OS loss) measured by SD-OCT, retinal sensitivity measured by Macular Integrity Assessment (MAIA) microperimetry, reading speed using the International Reading Speed Texts (IReST) Worksheets developed by the IReST Study Group [14], and participant responses to the NEI-VFQ-25 questionnaire, which is described below.

International Reading Speed Texts (IReST)

The International Reading Speed Texts (IReST) consists of paragraphs of text (approx. 130 words per text) - according to the everyday life reading demands with the same difficulty, content and linguistic characteristics in the different languages. It consists of a set of ten equivalent texts in each language for repeated measurements and international studies and was already evaluated in 425 normal young

subjects. Reading speed is calculated as the number of words read per minute.

Visual Function Questionnaire-25

The Visual Function Questionnaire-25 (VFQ-25) is a reliable 25-item version of the 51-item National Eye Institute Visual Function Questionnaire (NEI-VFQ). The survey measures health-related quality of life relevant to participants with vision disorders. The test is designed to capture the influence of vision on emotional well-being and social functioning dimensions. Response category for each item ranges from either 1 to 5 or 1 to 6. Each item will then convert to a 0 to 100 scale so that the lowest and highest possible scores are set at 0 and 100 points, respectively. In this format scores represent the achieved percentage of the total possible score (e.g., a score of 50 represents 50% of the highest possible score). Then, items within each sub-scale are averaged together to create the 12 sub-scale scores. The following table indicates which items contribute to each specific sub-scale. Items that are left blank (missing data) are not considered when calculating the scale scores. Sub-scales with at least one item answered can be used to generate a sub-scale score. Hence, scores represent the average for all items in the sub-scale that the respondent answered.

Scoring Key

Item Number	Response Category	Conversion (scores)
1, 3, 4, 15c	1	100
	2	75
	3	50
	4	25
	5	0
2	1	100
	2	80
	3	60
	4	40
	5	20
	6	0

Item Number	Response Category	Conversion (scores)
5, 6, 7, 8, 9,10, 11, 12, 13, 14,16, 16a	1	100
	2	75
	3	50
	4	25
	5	0
	6	Missing
17, 18, 19, 20, 21, 22, 23,24, 25	1	0
	2	25
	3	50
	4	75
	5	100

Sub-scales

Scale	Items to be averaged
General Health	1
General Vision	2
Ocular Pain	4, 19
Near Activities	5, 6, 7
Distance Activities	8, 9, 14
Social Functioning	11, 13
Mental Health	3,21,22,25
Role Difficulties	17, 18
Dependency	20, 23, 24
Driving	15c, 16, 16a
Color Vision	12
Peripheral Vision	10

The near activities subscale score is the measurement that will be used as a secondary outcome measure for the SAP.

4.4.2 Safety Variables

Safety will be evaluated by monitoring AEs and SAEs, results of ophthalmic examinations (including slit-lamp biomicroscopy and dilated fundus parameters, as well as measurements of BCVA and intraocular pressure [IOP]).

All AEs will be captured whether or not considered to be related to the surgical procedure, implant, or CNTF. The incidence of reported AEs will be compared between the treated and sham participants, particularly with respect to ocular AEs. An attempt will be made to differentiate between treatment-

related AEs and AEs considered to be part of the normal progression of the disease. In addition, for treatment-related AEs, an attempt will be made to differentiate those that the investigator believes are due to the device itself, to CNTF, or to the implant/sham procedure.

5 SAMPLE SIZE CONSIDERATIONS

Sample size calculation is based on the comparison of the 2 groups over 24 months (720 days) incorporating a longitudinal mixed effects model. The number of participants, N, in each of the 2 groups [15] is calculated as follows: We assume that, in the NT-501 implant group, the response of change in EZ area is as follows:

$$Y_{ij} = \beta_{0NT-501} + \beta_{1NT-501}x_{ij} + \varepsilon_{ij}, \quad j = 1, \dots, n; i = 1, \dots, m$$

For the sham group the sham equation holds as follows:

$$Y_{ij} = \beta_{0Sham} + \beta_{1Sham}x_{ij} + \varepsilon_{ij}, \quad j = 1, \dots, n; i = 1, \dots, m$$

Both groups have the same number of participants (m), $x_{ij} = x_j$ represents the duration between the first and the jth visit in which case β_{1Sham} and $\beta_{1NT-501}$ represents the rates of change in Y for Sham and NT-501 implant, respectively, and each person is measured at the same time points, and each participant has n repeated observations of EZ area planned to occur at baseline, 12, 16, 20 and 24 months (where months will be converted to years).

The number of participants, m, in each of the 2 groups [15] is calculated as follows:

$$m = \frac{2(z_{\alpha} + z_{\beta})^2 \sigma^2 (1 - \rho)}{ns_x^2 d^2}$$

where $d = \beta_{1Sham} - \beta_{1NT-501}$ and s_x^2 is the within-subject variance of x_j .

Using the above equation with a Type 1 error rate of 0.05 (2-sided); variance of endpoint (σ^2)= 0.0256; correlation between within participant observations (ρ) = 0.6; $s_x^2 = 0.47$ and n = 5 (baseline and 12, 16, 20 and 24 months) we have 80% power with a sample size of 50 participants per treatment group to detect a difference in rate of change 0.037 mm²/year in the EZ area in the NT-501 implant group versus the sham group. The sample size will be increased to 56 participants per treatment group (112 total participants) to provide adequate power in the analysis of the population evaluable for efficacy.

The statistical model will be a random intercept model as follows:

$$Y_{ij} = (\beta_0 + b_{0i}) + \beta_1 * TRT + \beta_2 * TIME + \beta_3 * TRT * TIME + \varepsilon_{ij}$$

where Y_{ij} is the efficacy endpoint (EZ area) measurement for participant $i = 1, 2, \dots, n$ at time point $j = 1, \dots, K$. TRT is an indicator of the participant i 's treatment group (i.e., TRT = 1 for NT-501 implant; TRT = 0 for sham) and TIME is the annualized time. To compare the rate of change from baseline in EZ area between the 2 treatment groups the primary hypothesis is as follows:

$$H_0: \beta_3 = 0 \text{ versus } H_1: \beta_3 \neq 0$$

5.1.1 Rationale for Parameters Used in Power Estimation

The NTMT-02 (Phase 2) allowed for the inclusion of both eyes in the study. If both eyes were eligible the right eye was randomized (1:1) to receive the NT-501 implant or sham procedure and the left eye received the alternative (surgery/sham). The sample size calculated above was based on estimates from an analysis incorporating NTMT-02 study design. Assuming independence between eyes the variance estimate (σ^2) is higher, yet the ρ is much higher with an estimate of power slightly higher 80%. Given the design of the NTMT-03A we assume similar estimates as those found in analysis assuming independence between eyes.

6 SUMMARY OF MODIFICATIONS

6.1 Modifications from the Approved Statistical Analysis Plan

This is the fourth version of the SAP for the Final Analysis. The major changes to this version include changes to the description of the secondary endpoints because of the addition of two study visits, Month 36 and Month 48, with amendment 5 of the study protocol. An additional change was made to the criteria for including in the per protocol analysis. This change has been added because of the marked increase in missed and out-of-window visits due to the COVID-19 pandemic.

7 GENERAL STATISTICAL CONSIDERATIONS

7.1 General Principles

All continuous variables at baseline and in terms of changes from baseline will be summarized using the following descriptive statistics: N (total number of participants in the population), n (total number of participants in the population with a given condition), mean, standard deviation (SD), median, maximum and minimum. Precision of the measurement for each continuous variable will be used to determine the number of decimal places to present in tables, figures, and derived listings. If the measurements in the source (raw) data are integers, the corresponding mean and median will be presented in 1 decimal place and the SD in 2 decimal places; if the measurements are in 1 decimal place, the mean and median will be in 2 decimal places and the SD in 3 decimal places; and so forth. Minimum and maximum will be displayed as reported in the source (raw) data. Any values that require transformation to standard units (metric or SI) will be converted with the appropriate corresponding precision. The frequency and proportion of observed levels will be reported for all categorical measures. Categorical variables will be summarized using counts and percentages. Percentages will be presented to 1 decimal place unless otherwise specified in the statistical programming document for the study.

When appropriate, corresponding exact 95% confidence intervals will be included. In general, all data will be listed, sorted by site, treatment group and participant, and by visit number within participants when appropriate. All summary tables will be structured with a column or row for each treatment group. Descriptive summaries of study endpoints across each visit will be presented in tables by treatment group. Inferential summaries of study endpoints in which formal statistical testing is implemented will be performed and presented by treatment group. Descriptive graphical summaries of study endpoints will be presented by treatment group and visit. In general, all data will be listed, sorted by site, treatment and participant, and when appropriate by visit number within participant.

The baseline value will be defined as the most recent non-missing measurement collected during a screening visit. For example, if a participant was re-screened for the study, the baseline value will be the 2nd screening value. The change from baseline value will be defined as post-baseline value minus baseline

value. These definitions will apply to all analysis variables: demographics, background, baseline characteristics, efficacy and safety, unless otherwise specified.

Unscheduled measurements will be recorded as such and not attributed to a scheduled measurement time point, unless otherwise specified. Where applicable, visit windows for efficacy analysis are presented in the relevant section.

Incomplete/Missing data: Missing post-baseline values will not be imputed for the primary efficacy analysis conducted using longitudinal mixed effects methods, which make use of all available data even if a participant has missing data at some post-baseline visits. For some endpoints, sensitivity analysis including imputation may be conducted. Where applicable, these analyses have been indicated in Section 9.1.1.

For safety analysis, no imputation will be used. Missing data (e.g., dates) will remain as missing, and conservative conventions established, as required. These will be documented in the statistical programming document for this study.

No formal statistical analyses will be performed to detect and/or remedy the presence of statistical outliers.

Measurements recorded more than once at a certain time point are defined as replicate observations. If a measurement is replicated and both are valid, the first recorded measurement will be used for analysis. Replicated measurements are expected for the baseline MAIA.

Measurements recorded for the same participant at different time points are defined as repeated observations. If an assessment has planned repeated measurements, then statistical summaries will present all planned time points, as appropriate (e.g., EZ area loss).

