#### **5.4 PARTICIPANT SCREENING**

Potential participants will be consented prior to initiation of any screening procedures. All screening procedures may be completed in 1 visit or may take place on more than 1 day if convenient for the participant or clinical site. All screening procedures should be completed within 30 days.

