9.2 Secondary Efficacy Analysis

The secondary endpoints will be analyzed using the mITT Population and the PP Population to test for superiority of NT-501 implant over sham. The secondary endpoints are listed below:

- Mean change in aggregate sensitivity of microperimetry within the EZ line break area from the Baseline Visit to the Month 24 Visit
- Mean change in reading speed from the Baseline Visit to the Month 24 Visit
- Mean change in the National Eye Institute Visual Function Questionnaire-25 (NEI-VFQ-25) near activities subscale score from the Baseline Visit to the Month 24 Visit

The observed change from Baseline visit to the Month-24 visit will be compared using t-tests. The analyses will be based on the actual values observed at the Baseline and the Month-24 visit efficacy assessment, regardless of timing of the visit as long as it occurs within +/- 30 days for pre-COVID period or within +119 days post-visit timepoint for COVID-related delays. The estimated mean treatment effect, a 95% confidence interval (CI), and a 2-sided p-value will be provided. No imputation of missing data will be done.

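### For baseline microperimetry the SAP keeps only the first of the replicate tests it expects; averaging them would sharpen the first-ranked secondary endpoint at almost no cost

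*SAP*

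**What the plan says.** SAP 7.1 contains two rules that bear on baseline microperimetry.

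- **Replicates.** "Measurements recorded more than once at a certain time point are defined as replicate observations". The rule for them is: "If a measurement is replicated and both are valid, the first recorded measurement will be used for analysis". The next sentence names one assessment: "Replicated measurements are expected for the baseline MAIA".
- **Baseline in general.** "The baseline value will be defined as the most recent non-missing measurement collected during a screening visit". The example is re-screening: "if a participant was re-screened for the study, the baseline value will be the 2nd screening value". The scope is wide but leaves room for exceptions: "These definitions will apply to all analysis variables: demographics, background, baseline characteristics, efficacy and safety, unless otherwise specified".

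Protocol 5.4 lets screening run over several days within a 30-day limit: "All screening procedures may be completed in 1 visit or may take place on more than 1 day". Protocol 7.2.1 lists microperimetry among the screening examinations without mentioning a replicate. Neither document says how many baseline MAIA tests are done, whether they share a day, or why the first is kept.

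Aggregate sensitivity stands first among the secondary endpoints in SAP 7.8. SAP 9.2 gives its analysis: "The observed change from Baseline visit to the Month-24 visit will be compared using t-tests".

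**The concern.** For the one assessment where replicates are expected, the stated rule uses one valid test and ignores the rest. A t-test on raw change carries the baseline measurement error into the result in full, so a single-test baseline is noisier than it needs to be.

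The endpoint's position makes this worth a sentence in the SAP. If the primary analysis succeeds but aggregate sensitivity misses 0.05, SAP 7.8 stops formal testing, and reading speed and the NEI-VFQ-25 near activities score are only described.

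The plan does average for the primary variable: SAP 9.1 defines EZ area as the mean of two readings. Those are two gradings of one image rather than two tests of the eye, so the parallel is loose, but it shows that averaging fits the plan's practice.

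**Working it through.** **The plan's own figure.** The only sizing calculation (Protocol 12.2, SAP 5) is for EZ area: m = 2(1.960 + 0.842)² × 0.0256 × (1 − 0.6) / (5 × 0.47 × 0.037²) = 49.97, so 50 per arm as stated. It is not affected. No variance, reliability, effect size or power is given for microperimetry.

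**Inputs from the documents.** One test is kept (SAP 7.1); raw change is compared by t-test (SAP 9.2); the two-sided level is 0.05 (SAP 7.8). Two tests are assumed because the replicate rule speaks of both being valid; the number is not stated.

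**Assumed inputs.** Test-retest reliability R from 0.6 to 0.95; correlation c between true scores at baseline and Month 24 from 0.7 to 1.0.

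**Variance of change.** Scale the variance of a single test to 1, with true-score variance R and error variance 1 − R at both visits.

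- One baseline test: V1 = 2R(1 − c) + 2(1 − R)
- Mean of two tests with independent errors: V2 = 2R(1 − c) + 1.5(1 − R)
- Proportional reduction: 0.5(1 − R)/V1

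For power, take as reference a comparison that has 80% with one baseline test. With the mean of two it has Φ(2.802/√(V2/V1) − 1.960). The 80% is a yardstick, not a plan figure.

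| R | c | V1 | V2 | Variance cut | SD cut | Power, from 80% |
|---|---|---|---|---|---|---|
| 0.95 | 0.7 | 0.670 | 0.645 | 3.7% | 1.9% | 81.5% |
| 0.9 | 0.8 | 0.560 | 0.510 | 8.9% | 4.6% | 83.5% |
| 0.8 | 0.9 | 0.560 | 0.460 | 17.9% | 9.4% | 87.1% |
| 0.6 | 0.9 | 0.920 | 0.720 | 21.7% | 11.5% | 88.6% |
| 0.8 | 1.0 | 0.400 | 0.300 | 25.0% | 13.4% | 89.9% |

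At c = 1 the cut is 25% for any R below 1, because all variance in change is then test error. That is the ceiling for two tests.

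**First against most recent.** Each is a single test, so with equal error variances both give V1. A simulation at R = 0.8 and c = 0.9 gives 0.560 for the first test, 0.559 for the last and 0.459 for the mean, matching the formulas.

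**Correlated replicate errors.** If the two baseline errors correlate at r, the reduction becomes 0.5(1 − r)(1 − R)/V1. At r = 0.5 (assumed) it is exactly half: 3.7% becomes 1.9% and 25% becomes 12.5%. Reference power is then Φ(2.802/√0.981 − 1.960) = 80.7% to Φ(2.802/√0.875 − 1.960) = 85.0%.

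**Baseline adjustment.** With baseline as a covariate, residual variance is 1 − R²c² for one test and 1 − 2R²c²/(1 + R) for the mean of two. At R = 0.8 and c = 0.9 these are 1 − 0.5184 = 0.4816 and 1 − 0.576 = 0.424, a cut of 12.0% against 17.9% for raw change.

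**Bias.** Baseline tests precede treatment and the arms are randomised, so baseline error has the same expectation in both. The loss is in precision only.

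**The case against.** A single pre-specified baseline test is a legitimate choice. It matches the single test expected at Month 24, leaves type I error alone, and does not bias the comparison. The number, timing and purpose of the replicates are not stated. Protocol 7.1 refers examination details to procedure-specific instructions that are not part of these documents, so we cannot confirm that the tests are interchangeable. Tests done close together may share error, which weakens the gain. Protocol 12.3.2 and SAP Appendix B name a mixed model rather than t-tests, so the variance figures hold only for the SAP 9.2 analysis. All of this stands, and it limits the size of the gain. It does not supply a reason to discard a valid test.

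Three stronger readings are tempting, and the documents do not support them.

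- *The SAP contradicts itself on baseline.* The most-recent rule is illustrated by re-screening and gives way where something else is specified. It can be read as choosing the screening occasion, with the replicate rule choosing within it. What remains is narrower: if two MAIA tests fall on different days of one screening period, it is unclear whether they are replicates (use the first) or successive screening values (use the last).
- *The clash of rules causes the noise.* It does not. First and last are each one test with the same variance; only averaging helps.
- *The baseline could be picked after the data are seen.* The replicate rule is fixed in advance, MAIA is named directly after it, and the SAP is to be approved before lock. The unclear case should be closed, but the text does not leave a free choice.

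The documents mention no learning effect for MAIA. If there were one, it would not favour keeping the first test.

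**Conclusion.** The point holds as a cheap improvement, not as an error in the plan. SAP 7.1 discards a valid baseline measurement for the endpoint that decides whether the other two secondary endpoints are formally tested.

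Under the assumed reliability and correlation, with two tests, independent errors and a t-test on raw change, averaging would reduce the variance of the change by about 4% to 25%. The top of that range needs every participant to have the same true change, which is unlikely in a progressive disease. With replicate errors correlated at 0.5 the range is about 2% to 12.5%, and baseline adjustment would lower it again. The documents cannot narrow these ranges. The primary analysis and its sample size are untouched.

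**What to change.** In SAP 7.1:

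1. Define baseline MAIA as the mean of all valid tests at the most recent screening occasion, counting all days of that screening period as one occasion.
2. State that this overrides the first-recorded rule for MAIA. This also settles precedence for tests on different days, and a re-screened participant still takes the value from the second screening.
3. State how many baseline MAIA tests are expected and when they are done.
4. Report the analysis with the first-test baseline as a sensitivity analysis.

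The cost is a few sentences and one extra table. No new data are needed, since the tests are already expected, and the SAP Preface allows amendment up to database lock. The one small downside is that an average still carries part of any learning effect, expected equally in both arms.

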7.2 Timing of Analyses

All final, planned analyses identified in this SAP will be performed only after the last participant has completed the Month 24 study visit and all relevant study data have been processed and integrated into the analysis database. In addition, no database may be locked or analyses completed until this SAP has been approved.

7.3 Populations

Assignment of participants to Populations will be done prior to the final data lock for the study. The following Populations will be defined: Population modified Intent to Treat (mITT) Set, Per Protocol Population Set, and Safety Population Set.

The analysis of baseline characteristics and efficacy endpoints will be performed on the mITT Population Set as defined below in Section 7.3.1. The primary efficacy analysis will also be performed on the Per Protocol Set as an additional sensitivity analysis. All safety analyses will be performed on the Safety Set.

7.3.1 Modified Intent-to-Treat Population

The Population mITT Set will include all randomized participants who received surgery (NT-501 implant or sham surgery) whether or not the participant adhered to the study protocol. Participants will be analyzed according to the treatment group to which they were randomized. All analyses of efficacy and non-safety (e.g., demographics) parameters will reference the mITT Population, as appropriate.

7.3.2 Per Protocol Population

The Per Protocol (PP) Population will be a subset of the mITT Population and will include all available data from participants who follow the protocol without major protocol violations(s). Major protocol violations are defined as deviations that may have a substantial impact on efficacy assessments. The criteria to be used for excluding participants from the PPS will be determined and documented before the final database lock. Participants will be analyzed according to the treatment group to which they were randomized. The PP Population will be used to perform supportive analyses of the primary and secondary endpoints.

7.3.3 Safety Set

The Safety Population will be defined as all participants who were randomized and received surgery (NT-501 implant or sham surgery) and have at least 1 safety measurement. Participants will be analyzed according to the group according to the treatment received, and no participants (or data) will be excluded from this dataset because of protocol violations that occur during the study. All analyses of safety will be conducted using the Safety Set.

